#### Sample Size

The sample size will range from 6-22 evaluable patients. The expected accrual rate will be approximately 1-2 patients / month for this patient population, thus requiring up to 22 months to complete the accrual.

#### Secondary endpoints

All secondary endpoints will be reported descriptively. This includes median number of days of ivosidenib tolerated, cumulative incidence of acute GVHD, cumulative incidence of significant chronic GVHD, and Kaplan-Meier estimates of overall and relapse-free survival. All laboratory correlative measurements will also be reported descriptively.

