### 1.2 Primary Objectives

To identify the recommended phase 2 dose (RP2D) of ivosidenib in patients with *IDH1*-mutant myeloid neoplasms after hematopoietic stem cell transplantation.

To explore the safety and tolerability of ivosidenib in patients with *IDH1*-mutant myeloid neoplasms in the post-stem cell transplant setting.

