**Treatment may not begin without confirmation from the Coordinating Center that the participant has been registered.**

### **5. TREATMENT PLAN**

#### **5.1 Treatment Regimen**

Ivosidenib will be administered orally every day for 28 consecutive days, defined as a treatment cycle. Appropriate dose modifications are described in Section 6. Reported adverse events and potential risks are described in Section 7. No investigational or commercial agents or therapies other than those described below may be administered with the intent to treat the participant's myeloid malignancy.

---

CONFIDENTIAL

This document is confidential. Do not disclose or use except as authorized.

The starting dose of ivosidenib (AG-120) will be 500mg orally daily. After 3 (or 6) participants are treated at 500mg daily, if this dose is tolerated, then an additional 10 participants will be treated at 500mg daily. If the 500mg daily dose is NOT tolerated in the initial cohort of participants, then the dose will be decreased to 250mg daily. If 250mg daily is tolerated, then an additional 10 participants will be treated at 250mg daily. The only doses studied will be 500mg daily and 250mg daily (the latter, if necessary).

The first cohort will consist of three participants. After the third participant is enrolled to the cohort, enrollment will be put on hold until all three participants have completed the first 28-day cycle. The period for dose-limiting toxicity (DLT) evaluation is the first 28-day cycle. Individual participants must receive at least 50% of the dosing to be DLT evaluable for that cohort. If this criteria is not met, the patient in that dose-escalation cohort may be replaced.

If one of three participants in a cohort experiences a DLT, then an additional 3 participants will be observed at that dose. The recommended phase 2 dose (RP2D) is defined as the highest dose level at which 0 or 1 of six participants experiences a dose-limiting toxicity.

Dose Escalation Schedule	
Dose Level	Dose of Ivosidenib
Level 1	250mg daily
Level 2 – Starting Dose	500mg daily

Once the RP2D is defined, an additional 10 participants will be enrolled at that dose.

If 250mg daily dosing is not tolerated, then the study will end without expansion.

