### 5.2.2 Subsequent Cycles

Subsequent cycles will require study visits within the first week of ivosidenib therapy, but will not require specific evaluations to begin the cycle given the continuous dosing nature of this study. A total of 12 cycles will be administered.

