## **5.6 Criteria for Taking a Participant Off Therapy**

Participants with persistent remission can continue receiving ivosidenib for 12 cycles.

Duration of therapy will depend on tolerance and evidence of disease progression. In the absence of treatment delays due to adverse event(s), treatment may continue for 12 cycles or until one of the following criteria applies:

- Disease progression
- Intercurrent illness that prevents further administration of treatment
- Unacceptable adverse event(s)
- Participant demonstrates an inability or unwillingness to comply with the oral medication regimen and/or documentation requirements
- Participant decides to withdraw from the protocol therapy
- General or specific changes in the participant's condition render the participant unacceptable for further treatment in the judgment of the treating investigator

Participants will be removed from protocol therapy when any of these criteria apply. Alternative care options will be discussed with the participant. The reason for removal from protocol therapy, and the date the participant was removed, must be documented in the case report form (CRF). The DF/HCC research team will update the relevant Off Treatment/Off Study information in the CTMS, OnCore. The Coordinating Center will update this information for external site participants.

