### 6.3.2 500 mg dosing

If the participant was at the 500mg daily dosing level when the toxicity occurred, and the toxicity resolves to  $\leq$  grade 1 *after* 14 days, but *before* 28 days (total) have elapsed, then dosing with ivosidenib can resume at the reduced dose of 250 mg daily. If the attributable toxicity recurs at  $\geq$  grade 3 (or grade 4 bilirubinemia in those with known Gilbert's disease – see above section 6.3) during the course of the study, then the participant will come off treatment and will remain on study only for survival and other outcomes.

If the participant was at the 500mg daily dosing level when the toxicity occurred, and it takes *less than* 14 days for the event to resolve to  $\leq$  grade 1, then dosing with ivosidenib can resume at 500mg daily. If the toxicity recurs at  $\geq$  grade 3 (or grade 4 bilirubinemia in those with known Gilbert's disease – see above section 6.3), then dosing will again be held. (This will be a DLT if it occurs during cycle 1). If the toxicity again resolves to  $\leq$  grade 1 within 28 days, then dosing with ivosidenib can resume at the reduced dose of 250mg daily. If the toxicity recurs yet again at  $\geq$  grade 3 (or grade 4 bilirubinemia in those with known Gilbert's disease – see above section 6.3), then the participant will come off treatment and will remain on study only for survival and other outcomes.

A participant who starts at 500mg daily dosing and is subsequently reduced to 250mg daily dosing due to toxicity can potentially increase back up to 500mg daily dosing if subsequent evaluation of the observed toxicity indicates no relation to study drug. Any such re-escalation must have the approval of the principal investigator, [name].

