### 6.4 Concurrent Use of CYP3A4 Inhibitors, CYP3A Inducers, and CYP3A Substrates

Dose adjustment of ivosidenib will be necessary when strong CYP3A4 inhibitors (listed in Appendix E) are initiated or used concurrently, given that concomitant administration with strong CYP3A4 inhibitors is predicted to increase ivosidenib steady-state C max by up to 52% and AUC by up to 90%. For patients at an ivosidenib dose of 500mg daily, concomitant use of strong CYP3A4 inhibitors, the ivosidenib dose will be reduced to 250mg daily, with close monitoring for any toxicity or QT interval prolongation.

The concomitant use of CYP3A inducers (listed in Appendix E) should be avoided. As for concomitant use of CYP3A substrates, this should be avoided when possible, but when this is medically necessary, very close monitoring for toxicity is needed. As an example, tacrolimus and sirolimus are both common immunosuppressive medications, and CYP3A substrates, that post-transplant participants may be taking. Both of these agents will be monitored closely in terms of trough levels, with levels will be doses closely followed and adjusted.

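### The only named summary of time on drug beyond cycle 1, a median of days tolerated, is undefined and can sit at its 336-day ceiling while 7 of 16 participants stop for toxicity

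*Combined protocol and SAP*

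**What the plan says.** Section 1.2 lists tolerability in a primary objective: "To explore the safety and tolerability of ivosidenib in patients with" this disease in the post-transplant setting. It gives no time frame.

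Section 13, under Secondary endpoints, states "All secondary endpoints will be reported descriptively" and then "This includes median number of days of ivosidenib tolerated". It gives no start or stop rule, no handling of censoring or competing events, and no condition on dose. Section 11.4 (Endpoints) defines overall and relapse-free survival but not this quantity.

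The sections that determine what the number would measure are these:

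- **Length of treatment.** Section 5.1: "Ivosidenib will be administered orally every day for 28 consecutive days, defined as a treatment cycle". Section 5.2.2: "A total of 12 cycles will be administered".
- **Reasons for stopping.** Section 5.6: "Duration of therapy will depend on tolerance and evidence of disease progression". Its list also includes intercurrent illness, non-compliance, withdrawal and investigator judgment, alongside unacceptable adverse events. The reason and date go on the case report form.
- **Held days.** The opening of Section 6 lets the cycle day run on while drug is held.
- **Reduced dose after toxicity.** Section 6.3.2 provides that after certain toxicities at 500 mg, "then dosing with ivosidenib can resume at the reduced dose of 250 mg daily". Section 6.7.2 has the same provision for hematologic toxicity.
- **Reduced dose for a drug interaction.** Section 6.4 provides that with a strong CYP3A4 inhibitor, "the ivosidenib dose will be reduced to 250mg daily".

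**The concern.** The dose is chosen on toxicity in cycle 1 alone, but participants may take the drug for 12 cycles. Whoever plans the later phase II study will want to know how many participants stopped or were cut back because of the drug, and when. The one named statistic that speaks to staying on treatment over that period does not answer this clearly.

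There are two separate problems. The first is that the term has no definition, so two analysts could compute different numbers from the same data. The second is that its plainest reading, days on drug, has a ceiling and combines events with different meanings. In a population treated to prevent relapse, a stop for relapse shortens time on drug without showing intolerance. A participant kept on drug at half the assigned dose after toxicity lengthens it without showing tolerance of that dose.

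**Working it through.** **Inputs.** Cycle length is 28 days (Section 5.1) and there are 12 cycles (Section 5.2.2). The group at the recommended dose is 16: 6 from dose finding plus 10 in expansion (Section 13). The documents give no relapse or discontinuation rates, so every event pattern below is an assumption.

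**The plan's own figure first.** No precision is stated for the median. The nearest stated figure is the 90% confidence interval for the toxicity rate at n = 16, within ±22%. The exact (Clopper-Pearson) interval at 8/16 runs from 27.9% to 72.1%, a half-width of (72.1 − 27.9)/2 = 22.1 points. The figure reproduces.

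**Ceiling.** 12 × 28 = 336 days. With 16 participants the median is the mean of the 8th and 9th ordered values. Suppose k participants stop for toxicity at day 28 and the rest finish:

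| Toxicity stops k | Proportion | Median days |
|---|---|---|
| 7 | 44% | 336 |
| 8 | 50% | (28 + 336)/2 = 182 |
| 9 | 56% | 28 |

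The median does not move for any k from 0 to 7, then falls by more than 300 days between k = 7 and k = 9. For k up to 7 the day of stopping is irrelevant. If held days were left out, finishers could fall somewhat below 336, but with k = 7 the 8th and 9th values still belong to finishers, so the early stops remain invisible.

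**How often the ceiling is reached.** The median equals 336 when at least 9 of 16 finish. Take assumed independent 12-cycle risks, counting only toxicity and relapse stops:

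- Toxicity 10%, relapse 20%: chance of finishing 0.90 × 0.80 = 0.72, and P(at least 9 of 16) = 95%.
- Toxicity 30%, relapse 20%: chance of finishing 0.70 × 0.80 = 0.56, and P(at least 9 of 16) = 59%.

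Three times the toxicity risk would still most often be reported as a median of 336.

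**Mixed causes, on the days-on-drug reading.** If nobody stops for toxicity, 9 relapse at day 150 and 7 finish, the median is 150. The toxicity discontinuation rate is 0/16.

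**Dose reduction, on the same reading.** If all 16 start at 500 mg, are cut to 250 mg from day 29 and finish, the median is 336. Relative dose intensity is (28 × 500 + 308 × 250)/(336 × 500) = 91,000/168,000 = 54%. The same 54% would arise if every cut were for a CYP3A4 inhibitor, which is not intolerance. Dose intensity therefore needs to be split by reason.

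**What a cause-specific summary would show.** With every participant followed to a stop or to the end of cycle 12, the cumulative incidence of toxicity discontinuation is a simple proportion: 7/16 = 44% in the first row of the table, and 0/16 = 0% in the relapse example. The exact 90% intervals are 22.7% to 66.7% and 0% to 17.1%.

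**The case against.** The strongest reply is that the documents do not say relapse counts as intolerance or that reduced-dose days count as tolerated. An analyst could censor relapse stops or count only days at the assigned dose. That is right. Those two faults depend on reading the term as days on drug, and the documented defect is the missing definition.

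Second, the median does not carry tolerability alone. Section 13 plans a toxicity rate with a confidence interval and evaluates toxicity in everyone treated, Section 1.3 calls for related toxicities by severity, and reasons for stopping are collected. This also stands, and it limits the point to time on drug beyond cycle 1. It does not remove it: the dose-limiting toxicity counts cover cycle 1, the toxicity rate has no stated time window, and no analysis of the stop reasons is named.

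Third, a reader might infer that the statistic could place a poorly tolerated dose above a well tolerated one. The documents do not support that. The total is 6 to 22 evaluable patients, so two groups of 16 cannot exist. The 250 mg level opens only after 500 mg has been rejected on dose-limiting toxicities, and no comparison of doses on this median is planned.

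Finally, this is a descriptive secondary summary with no test or decision attached. That bears on how much the point matters, but not on whether the number informs.

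**Conclusion.** The point holds in a limited form. The median is undefined and, because treatment ends at 336 days, it cannot distinguish 0 from 7 toxicity stops out of 16 when everyone else finishes. That result needs only the ceiling and the sample size. The mixing of relapse with intolerance, and the masking of holds and dose cuts, follow if the term is read as days on drug.

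The consequence is a weak description of longer-term tolerability, within a primary objective, handed to the planners of the next study. The recommended dose is unaffected because it rests on cycle 1 dose-limiting toxicities. The risks used to show how often the ceiling is reached are illustrative. This is an inexpensive improvement to the analysis plan and not a flaw in the design.

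**What to change.** In Section 13, Secondary endpoints:

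1. **Define the median if it is kept.** State the start and end dates, how relapse, death, withdrawal and completion are handled, and whether held and reduced-dose days count.
2. **Add a cumulative incidence** of first discontinuation or dose reduction for a drug-related adverse event. Treat relapse, death and other stops as competing events, with completion of 12 cycles as the end of risk. Using the first reduction avoids having to define a permanent one, since Sections 6.3.2, 6.5 and 6.7.2 allow re-escalation. State which attribution assessment applies, because Sections 6.3.2 and 6.7.2 let it be revised, and how stops for graft-versus-host disease (Sections 6.1 and 6.2) are classified.
3. **Report relative dose intensity** by assigned dose level, as mg taken over mg planned at that level between first and last dose. Show reductions for strong CYP3A4 inhibitors (Section 6.4) separately from toxicity reductions.

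No new visits are needed. Stop reasons and dates are already on the case report form (Section 5.6), the diary records each dose (Section 5.1), and the plan already uses cumulative incidence for graft-versus-host disease. The cost is a paragraph of wording and one descriptive table. Intervals at about 16 participants will be wide, as the 22.7% to 66.7% range for 7/16 shows.

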### **14. PUBLICATION PLAN**

---

CONFIDENTIAL

This document is confidential. Do not disclose or use except as authorized.

The results should be made public within 24 months of reaching the end of the study. The end of the study is the time point at which the last data items are to be reported, or after the outcome data are sufficiently mature for analysis, as defined in the section on Sample Size, Accrual Rate and Study Duration. If a report is planned to be published in a peer-reviewed journal, then that initial release may be an abstract that meets the requirements of the International Committee of Medical Journal Editors. A full report of the outcomes should be made public no later than three (3) years after the end of the study.

---

CONFIDENTIAL

This document is confidential. Do not disclose or use except as authorized.

**APPENDIX A      PERFORMANCE STATUS CRITERIA**

ECOG Performance Status Scale		Karnofsky Performance Scale	
Grade	Descriptions	Percent	Description
0	Normal activity. Fully active, able to carry on all pre-disease performance without restriction.	100	Normal, no complaints, no evidence of disease.
		90	Able to carry on normal activity; minor signs or symptoms of disease.
1	Symptoms, but ambulatory. Restricted in physically strenuous activity, but ambulatory and able to carry out work of a light or sedentary nature (e.g., light housework, office work).	80	Normal activity with effort; some signs or symptoms of disease.
		70	Cares for self, unable to carry on normal activity or to do active work.
2	In bed <50% of the time. Ambulatory and capable of all self-care, but unable to carry out any work activities. Up and about more than 50% of waking hours.	60	Requires occasional assistance, but is able to care for most of his/her needs.
		50	Requires considerable assistance and frequent medical care.
3	In bed >50% of the time. Capable of only limited self-care, confined to bed or chair more than 50% of waking hours.	40	Disabled, requires special care and assistance.
		30	Severely disabled, hospitalization indicated. Death not imminent.
4	100% bedridden. Completely disabled. Cannot carry on any self-care. Totally confined to bed or chair.	20	Very sick, hospitalization indicated. Death not imminent.
		10	Moribund, fatal processes progressing rapidly.
5	Dead.	0	Dead.

CONFIDENTIAL

This document is confidential. Do not disclose or use except as authorized.

### 1. INTRODUCTION

The Dana-Farber/Harvard Cancer Center Multi-Center Data and Safety Monitoring Plan (DF/HCC DSMP) outlines the procedures for conducting a DF/HCC Multi-Center research protocol. The DF/HCC DSMP serves as a reference for any sites external to DF/HCC that are participating in a DF/HCC clinical trial.

#### 1.1 Purpose

---

CONFIDENTIAL

This document is confidential. Do not disclose or use except as authorized.

To establish standards that will ensure that a Dana-Farber/Harvard Cancer Center Multi-Center protocol will comply with Federal Regulations, Health Insurance Portability and Accountability Act (HIPAA) requirements and applicable DF/HCC Standard Operating Procedures.

## **1.2 Multi-Center Data and Safety Monitoring Plan Definitions**

**DF/HCC Multi-Center Protocol:** A research protocol in which one or more outside institutions are collaborating with Dana-Farber/Harvard Cancer Center where a DF/HCC investigator is the sponsor. DF/HCC includes Dana-Farber/Partners Cancer Care (DF/PCC) Network Clinical Trial Affiliates.

**Lead Institution:** One of the Dana-Farber/Harvard Cancer Center consortium members (Dana-Farber Cancer Institute (DFCI), Massachusetts General Hospital (MGH), Beth Israel Deaconess Medical Center (BIDMC), Boston Children's Hospital (BCH), Brigham and Women's Hospital (BWH)) responsible for the coordination, development, submission, and approval of a protocol as well as its subsequent amendments per the DFCI IRB and applicable regulatory guidelines (CTEP, Food and Drug Administration (FDA), Office of Biotechnology Activities (OBA) etc.). The Lead Institution is typically the home of the DF/HCC Sponsor. The Lead Institution also typically serves as the Coordinating Center for the DF/HCC Multi-Center Protocol.

**DF/HCC Sponsor:** The person sponsoring the submitted Multi-Center protocol who takes responsibility for initiation, management and conduct of the protocol at all research locations. In applicable protocols, the DF/HCC Sponsor will serve as the single liaison with any regulatory agencies. The DF/HCC Sponsor has ultimate authority over the protocol and is responsible for the conduct of the study at DF/HCC and all Participating Institutions. In most cases the DF/HCC Sponsor is the same person as the DF/HCC Overall Principal Investigator; however, both roles can be filled by two different people.

**Participating Institution:** An institution that is outside the DF/HCC and DF/PCC consortium that is collaborating with DF/HCC on a protocol where the sponsor is a DF/HCC Investigator. The Participating Institution acknowledges the DF/HCC Sponsor as having the ultimate authority and responsibility for the overall conduct of the study.

**Coordinating Center:** The entity that provides administrative support to the DF/HCC Sponsor in order that he/she may fulfill the responsibilities outlined in the protocol document and DSMP, and as specified in applicable regulatory guidelines. In general, the Lead Institution is the Coordinating Center for the DF/HCC Multi-Center Protocol.

**DF/HCC Office of Data Quality (ODQ):** A group within DF/HCC responsible ensuring high-quality standards are used for data collection and the ongoing management of clinical trials, auditing, and data and safety monitoring. ODQ also coordinates quality assurance efforts related to multi-center clinical research.

**DF/HCC Clinical Trials Research Informatics Office (CTRIO):** A group within DF/HCC responsible for providing a comprehensive data management platform for managing clinical trial data.

## 2. GENERAL ROLES AND RESPONSIBILITIES

For DF/HCC Multi-Center Protocols, the DF/HCC Sponsor, the Coordinating Center, and the Participating Institutions are expected to adhere to the following general responsibilities:

### 2.1 DF/HCC Sponsor

The DF/HCC Sponsor, [name]. will accept responsibility for all aspects of conducting a DF/HCC Multi-Center protocol which includes but is not limited to:

- Oversee the coordination, development, submission, and approval of the protocol as well as subsequent amendments.
- Ensure that the investigators, study team members, and Participating Institutions are qualified and appropriately resourced to conduct the protocol.
- Include the Multi-Center Data and Safety Monitoring Plan as an appendix to the protocol.
- Ensure all Participating Institutions are using the correct version of the protocol.
- Ensure that each participating investigator and study team member receives adequate protocol training and/or a Site Initiation Visit prior to enrolling participants and throughout trial's conduct as needed.
- Ensure the protocol will be provided to each participating site in a language understandable to all applicable site personnel when English is not the primary language.
- Monitor progress and overall conduct of the study at all Participating Institutions.
- Ensure all DFCI Institutional Review Board (IRB), DF/HCC and other applicable (i.e. CTEP, FDA, OBA) reporting requirements are met.
- Review data and maintain timely submission of data for study analysis.
- Act as the single liaison with the FDA (investigator-held IND trials) as applicable.
- Ensure compliance with all requirements as set forth in the Code of Federal Regulations, applicable DF/HCC requirements, HIPAA requirements, and the approved protocol.
- Commit to the provision that the protocol will not be rewritten or modified by anyone other than the DF/HCC Sponsor.
- Identify and qualify Participating Institutions and obtain accrual commitments prior to extending the protocol to that site.
- Monitor accrual and address Participating Institutions that are not meeting their accrual requirements.

